## 3.7.4 Premature closure of trial sites

The sponsor has the right to close a trial site due to the following reasons:

- Major protocol violations
- Violations of legal and ethical regulations (GCP)
- Poor recruitment, no patients
- Non-compliance of investigator

## 3.7.5 Premature closure of the clinical trial

The following reasons the whole trial may be discontinued at the discretion of the sponsor:

- New risks for patients become known.
- Inefficacy of the trial medication becomes evident.
- Occurrence of AEs unknown to date in respect of their nature, severity, and duration or the unexpected increase in the incidence of known AEs.
- Medical or ethical reasons affecting disadvantageous the continued performance of the trial.
- Difficulties in the recruitment of patients.

The ethic committees (EC) and the competent authorities must then be informed. Should the trial be closed prematurely, all trial material (completed, partially completed, blank CRF, randomization envelopes, investigational medicinal products, etc.) must be returned to the sponsor or will be collected by the monitor.

# 4 TRIAL TREATMENTS

## 4.1 Investigational treatments

### 4.1.1 General information about investigational medicinal product (IMP)

#### Rasagiline (AZILECT®)

Drug code: International nonproprietary name (INN): Formulation: Manufacturer: Market authorization: Dosage authorized: N04BD02 Rasagiline 1 mg tablet Teva Pharma GmbH Yes, for the following indication: Parkinson's disease 1 mg/day

#### Placebo

Drug code: International nonproprietary name (INN): Formulation: Manufacturer: Dosage authorized: not applicable not applicable tablet Teva Pharma GmbH 1 tablet/day

#### *4.1.2 Therapeutic effects*

Rasagiline is a selective and potent irreversible monoaminooxidase (MAO)-B inhibitor. The precise mechanisms of action of rasagiline are unknown. One mechanism is believed to be related to its MAO-B inhibitory activity, which causes an increase in extracellular levels of dopamine in the striatum. The elevated dopamine level and subsequent increased dopaminergic activity are likely to mediate rasagiline's beneficial effects seen in models of dopaminergic motor dysfunction.

#### 4.1.3 Known side effects

The following information is based on the current version of the Summary of Product Characteristics (SmPC, December 2011). The investigators will be provided with updated versions of SmPC as soon as they become available.

Rasagiline was administered to approximately 1361 patients during all phase II/III clinical trials. The long-term safety profile was similar to that observed with shorter duration exposure. There were no significant differences in the safety profile based on age or gender.

#### Side effects with rasagiline monotherapy:

Very frequent ( $\geq 1/10$ ): Headache

Frequent ( $\geq$  1/100, <1/10)): Flu syndrome, skin carcinoma, leukopenia, allergic reaction, depression, hallucinations, conjunctivitis, vertigo, angina pectoris, rhinitis, flatulence, dermatitis, muscular pain, neck pain, arthritis, desire to urinate, fever, malaise

Infrequent (≥1/1.000, <1/100): Apoplexia, reduced appetite, vesiculobullous rash, myocardial infarction

### Warnings and precautions:

- Risk for Hypertensive Crisis and nonselective MAO inhibition above the recommended Doses
- Melanoma (Epidemiological studies have shown that patients with Parkinson's disease have a higher risk (2- to approximately 6-fold higher) of developing melanoma than the general population. Whether the increased risk observed was due to Parkinson's disease or other factors, such as drugs like rasagiline used to treat Parkinson's disease, is unclear)
- Rasagiline may cause lower blood pressure, especially postural hypotension or increase blood pressure in different patients
- Rasagiline may cause or exacerbate hallucinations or potentially other manifestations of psychotic-like behavior

#### 4.1.4 Treatment administration

Rasagiline (oral 1 mg/day) will be provided in bottles that contain enough tablets for 3 months and some reserve.

#### V1 (Baseline)

- A) 1 bottle with 110 tablets rasagiline, 1 mg
- B) 1 bottle with 110 tablets placebo matching rasagiline 1 mg

#### V2 (Month 2)

- A) 1 bottle with 110 tablets rasagiline, 1 mg
- B) 1 bottle with 110 tablets placebo matching rasagiline 1 mg

#### V3 (Month 6)

- A) 2 bottles with 110 tablets rasagiline, 1 mg
- B) 2 bottles with 110 tablets placebo matching rasagiline 1 mg

#### V4 (Month 12)

- A) 2 bottles with 110 tablets rasagiline, 1 mg
- B) 2 bottles with 110 tablets placebo matching rasagiline 1 mg

#### *4.1.5* Overdose instructions

Reported signs and symptoms of rasagiline overdosage in the range of 3 mg to 100 mg included, alone or in combination, any of the following: dysphoria, hypomania, hypertensive crisis and Serotonin-syndrome

There is no specific antidote for rasagiline overdose. The following suggestions are offered based upon the assumption that rasagiline overdose may be modeled after non-selective MAO inhibitor poisoning. Treatment of overdose with non-selective MAO inhibitors is symptomatic and supportive. Respiration should be supported by appropriate measures, including management of the airway, use of supplemental oxygen, and mechanical ventilatory assistance, as required. Body temperature should be monitored closely. Intensive management of hyperpyrexia may be required. Maintenance of fluid and electrolyte balance is essential. For this reason, in cases of overdose with rasagiline, dietary tyramine restriction should be observed for several weeks to avoid the risk of a hypertensive/cheese reaction.

## 4.1.6 Treatment assignment

The trial medication will be administered only to patients included in this trial. The medication will be given to the patient by the investigator or trial personnel that has been authorized by the investigator. If a patient misses one visit, the medication can be handed out to a relative or can be sent. If a patient misses more than one visit, the investigator should contact the sponsor in order to determine how to proceed.

Patients withdrawn from the trial retain their identification codes (e.g. randomization number). New patients will always receive a new identification code. Treatment after end of trial

At the end of the study patients will be informed about further treatment and further care options by the investigator.

## 4.1.7 Packaging and labeling

The trial medication will be packed by TEVA Pharma GmbH and labeled by the Pharmacy of the University Hospital UIm according to the randomization list.

The trial medication will be labeled according to §5 GCP regulation. The label contains at minimum the following details:

- For use in clinical trial only
- Name and address of the Sponsor
- Name and address of the CRO
- Name and dosage of investigational medication
- Batch number "Ch.-B. or code number",
- Administration form (tablets)
- Content specified by weight, volume or quantity (may be omitted or encoded for blinding reasons)
- Application form (p.o.)
- Expiry date using note "usable until"
- Storage conditions
- Keep away from children
- Patient ID, randomization number, or other code to identify the patient
- Protocol ID,
- EudraCT Number (if not contained in an accompanying document handed out to patients)

Additional statements will be printed on the label(s) as required by local regulations.

IMP assignment and traceability as required by GCP-V § 5 (1) will be realized by accurate documentation of drug accountability and compliance on an accompanying document.

#### *4.1.8 Drug storage, supplies and accountability*

The investigator will take inventory and acknowledge the receipt of all shipments of the trial medication. All trial medication must be kept in a locked area with access restricted to designated trial staff.

The trial medication must be dryly stored in accordance with manufacturer's instructions at temperatures of 25°C or below.

The investigator will also keep accurate records of the quantities of trial medication dispensed, used, and returned by each patient on the drug accountability form.

The site monitor will periodically check the supplies of trial medication held by the investigator to verify the correct accountability of all trial medication used. At the end of the trial, all unused trial medication and all medication bottles will be completely returned to the pharmacy in case no other procedure is agreed.

It will be assured that a final drug accountability report is prepared and maintained by the investigator.

*4.1.9 Procedures for monitoring patient compliance* 

Trial medication will be dispensed to the patients by the investigator.

Patients will be instructed to bring all trial medication to the trial site at every visit (including all empty bottles and unused trial medication). Compliance will be assessed by counting of the remaining tablets. Details will be recorded in the CRF and on the drug accountability form in the investigator site file.

## 4.2 Not permitted medication

The following concomitant treatments are not permitted during the trial: (Contraindications for rasagiline)

- Meperidine, tramadol, methadone or propoxyphene
- Dextromethorphan, St. John's wort or cyclobenzaprine
- Sympathomimetic amines, including amphetamines as well as cold products and weightreducing preparations that contain vasoconstrictors (e.g., pseudoephedrine, phenylephrine and ephedrine).
- Serotonin reuptake inhibitors (SSRIs), including fluoxetine or fluvoxamine.
- Serotonin noradrenalin reuptake-inhibitors (SNRIs)
- Tricyclic and tetracyclic antidepressants
- Other MAO inhibitors (selective or non-selective)

Surgery: As with other MAO inhibitors, patients taking rasagiline should not undergo elective surgery requiring general anesthesia. Also, they should not be given local anesthesia containing cocaine or sympathomimetic vasoconstrictors. Rasagiline should be discontinued at least 14 days prior to elective surgery. If surgery is necessary sooner, benzodiazepines, mivacurium, fentanyl, morphine, and codeine may be used cautiously.

# 5 TRIAL SCHEDULE

## 5.1 Trial visits schedule

For the planned trial visits schedule the inclusion date is considered to be the reference date. The dates of the following visits specified in the protocol are calculated in relation to the date of this visit.

If the time of a visit is modified in relation to the visits schedule, the times of the following visits will always be determined with respect to the inclusion visit. The time window for each planned visit will be  $\pm$  one week. The investigator must always ensure that the patient receives a sufficient quantity of treatment units to cover the period up to the next visit. The visits schedule is not modified by any unscheduled visits.

In the case of premature interruption of the study treatment, a complete examination identical to visit V5 should be carried out. Premature study discontinuation must be noted as such on the case report form. Patients prematurely leaving the study must not rejoin the trial.

Additionally a study physician will contact the patient by telephone 1, 3, 9, and 15 months after study enrolment.

An overview including the time schedule and evaluations for all visits is given on page 5. Evaluations performed at the study visits comply with the routine assessments for ALS patients, except that evaluations in patients outside of the clinical trial are performed less often (approximately twice a year).

Venous blood samples taken during the visits will be destroyed after determination of the required parameters. Only the samples collected for genetic testing will be stored and used as outlined in section 6.3.3. of the protocol.

#### Screening visit (V0)

A signed "Informed Consent" will be obtained from each patient prior to initiating any trial procedure. Presence of ALS diagnostic criteria will be documented as well as site of onset and ALS status at entry according to the revised El Escorial criteria. Venous blood will be taken for the determination of blood cell count, creatinine, CK, ASAT, ALAT, blood glucose, and HCG or urine pregnancy test (only in women with child bearing potential). The patients' eligibility will be determined in accordance with the inclusion/exclusion criteria. Demographics and a detailed medical history will be taken, and concomitant medication will be recorded. A physical examination, including body weight, height, blood pressure, and radial pulse will be performed. Additionally lung function will be assessed by measuring the patient's vital capacity.

### Baseline Visit 1 (V1)

Patients eligible for study participation will enter the study site within 4 weeks after the screening visit and will be randomized to one of the treatment arms.

Blood samples for the determination of blood cell count, creatinine, CK, ASAT, ALAT and blood glucose, will be obtained. A blood sample for genetic testing will be collected as outlined in section 6.3.3. if the patient provided consent to this analysis. Body weight, blood pressure and radial pulse will be documented and lung function will be assessed by measuring the patient's vital capacity. In addition ALSFRS-R and SEIQoL will be performed. The patient will receive study medication according to the randomization list and a study participant card (see appendix VIII).

Any changes in the concomitant medication and adverse events before and during visit 1 will be documented.

## Visit 2-4 – Control Visits (V2, V3, V4)

Visit 2, 3, and 4 will be performed 2, 6, and 12 months after visit 1 respectively.

Venous blood samples will be taken for the determination of blood cell count, creatinine, CK, ASAT, ALAT and blood glucose. Body weight, blood pressure and radial pulse will be documented and lung function will be assessed by measuring the patient's vital capacity. In addition ALSFRS-R, and SEIQoL will be performed. Patient will be asked for compliance and drug accountability will be performed. Additionally the patient will be supplied with new study medication. Any changes in the concomitant medication and adverse events will be documented.

#### Visit 5 – Final Visit (V5)

Visit V5 will be performed 18 months after visit V1. Any adverse events and changes in concomitant medication will be documented.

Blood samples will be taken for the determination of blood cell count, creatinine, CK, ASAT, ALAT and blood glucose. Body weight, blood pressure and radial pulse will be documented and lung

function will be assessed by measuring the patient's vital capacity. In addition ALSFRS-R and SEIQoL will be performed. The patient will be asked for compliance and will return the study medication of V4. Additionally drug accountability will be performed.

### Telephone contacts (T1 – T4)

At months 1, 3, 9, 15 the patient or its relative will be contacted by telephone to assess the following items:

- ALS FRS-R
- Weight
- Adverse events
- Changes in concomitant therapies
- Compliance to study drug regimen

If a patient misses a visit or telephone contact the subsequent visit or telephone contact will not be brought forward but will be performed on the scheduled day.

If a patient misses more than one visit, the investigator should contact the sponsor in order to determine how to proceed.

#### 5.2 Unscheduled visits

Unscheduled visits may be carried out at any time during the study in the case of a medical emergency, when a patient would like to report a medical problem or when the investigator considers this necessary for the patient's well-being. These unscheduled visits must be recorded on the case report form. In no case must they lead to a modification in the study visits schedule stipulated by the protocol.

#### 5.3 Visits following premature discontinuation of study treatment

If a patient discontinues participation in the study for whatever reason, every effort has to be undertaken to perform an early termination visit. In this case, the same investigations have to be performed as in visit V5.

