#### 3.7.3 Withdrawal criteria

Patients can withdraw their consent at their own request without given reasons at all times during the trial. This should be without disadvantages for the patient.

Whenever possible, all patients prematurely discontinuing study medication should perform an early termination visit including the same evaluations as scheduled for visit V5. The reason(s) for premature cessation of a patient's participation during the trial, other than death, should be specified on the case report form.

Study treatment may be stopped prematurely if any of the following events occur, according to the judgment of the investigator:

• Significant intolerance of the study medication, or significant clinical or laboratory findings, e.g. increase in ASAT or ALAT >3 times the upper limit of normal

- Significant intercurrent illness or emergency situation requiring cessation of the study
- The patient wishes to terminate his/her participation in the study
- Investigator judgment that it is in the best interest of the patient
- Failure to comply with the investigational procedures
- Pregnancy
- Technical reasons (change of physician, change of address of volunteer/patient)

Patients who have started double-blind treatment will not be replaced.

For any patient prematurely discontinuing the study, the investigator must:

- Recover all the treatment units given to the patients
- In as far as possible, carry out all the examinations and tests planned for the final visit after withdrawal of the patient from the study
- Fill in the corresponding pages of the case report form, specifying the date and reason for premature discontinuation
- When applicable, ask the patient the reason of his/her Informed Consent withdrawal while fully respecting the patient's rights
- Where possible prescribe a visit 2 weeks after withdrawal in order to control and document any change in the patient's clinical status. If a serious adverse event occurs, the Responsible Nominated Safety Contact must be informed according to the procedures described in section 6.2.2.5. "Immediate reporting of SAEs by investigator".
- All ongoing serious adverse events of withdrawn patients have to be followed up until no more signs and symptoms are verifiable or the investigator has assessed its sequelae, even after the end of the trial.

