## 6 TRIAL METHODS

#### 6.1 Assessment of efficacy

Efficacy variables:

- Survival / date of death requiring a death certificate
- ALSFRS-R
- SEIQoL
- sVC

The Efficacy variables listed above will be determined at the study site using standard methods.

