## 7.1 Sample size

The sample size calculation is based on a comparison of two survival curves using the one-sided log-rank test. Following assumptions were made: Type one error 0.025, power 0.80, recruiting time 6 months, length of follow up period 18 months, 18 month survival rate of 70 % in the control group, 18 month survival rate of 85 % in the experimental group. Under the assumption of equal number of patients in each group, this scenario requires 106 patients in each group, i.e.  $2 \times 106 = 212$  patients in whole trial.

A previous study [GERP ALS-Study; pioglitazone in ALS; NCT00690118, clinicaltrials.gov ID] showed a drop-out rate of about 15 %, screening failure was observed in about 10 %. Thus, in total 250 patients have to be allocated (with consideration of a drop-out rate) and a total number of 278 patients have to be assessed for eligibility.

The sample size calculation was performed using SAS® software, version 9.2, procedure power.

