### Replacement of missing values for ITT analysis:

Date of death will be known for all patients who will die during trial. For patients who are alive at end of study/last contact, the following replacement of missing date will be performed. Any date of last contact with unknown day (xx/NA/xxxx) in patients who are alive will be replaced with the date for mid-month (xx/15/xxxx). Dates of last contact with unknown day and month or with unknown day and month and year will not be replaced.

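### No survival follow-up to month 18 is specified for patients who stop treatment or leave early, although the sole confirmatory analysis is ITT on time to death

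*Protocol*

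**What the plan says.** **Leaving.** Protocol 3.7.3 asks patients who stop study medication early to have a termination visit with the V5 evaluations. Its reasons for stopping treatment include intolerance, non-compliance and a change of address, none of which is an objection to further contact. Section 5.1 attaches the V5 examination to interruption of treatment and adds that "Patients prematurely leaving the study must not rejoin the trial". The heading of 5.3 refers to treatment, but its text refers to participation: "If a patient discontinues participation in the study for whatever reason, every effort has to be undertaken to perform an early termination visit".

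**After leaving.** Section 3.7.3 says "Where possible prescribe a visit 2 weeks after withdrawal" and requires ongoing serious adverse events to be followed. Section 6.2.2.3 collects adverse events for 14 days after termination. The telephone contacts in 5.1 fall at months 1, 3, 9 and 15 and may reach a relative, but they are not stated to continue for patients who have left.

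**Endpoint.** Section 2.1 measures survival from randomisation to death or the end of the trial. Section 7.3.1 censors living patients at the study termination date or the last visit, whichever is later, without saying whether termination means the patient's own exit or the end of the trial. It also states: "Date of death will be known for all patients who will die during trial". Only the ITT analysis is confirmatory.

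**Planning rate.** Section 7.1 relies on an earlier ALS trial that "showed a drop-out rate of about 15" per cent. It does not say what counted as drop-out.

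**The concern.** An ITT comparison of mortality needs to know, for each randomised patient, whether and when death occurred within the planned period, on treatment or not. Here, stopping tablets can end observation of the endpoint itself. Sections 2.1 and 7.3.1 presuppose complete death ascertainment, while 3.7.3, 5.1, 5.3 and 6.2.2.3 provide none beyond about two weeks after exit.

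The undefined termination date does not resolve this. If it is the patient's own exit, the leaver is censored there and later deaths do not count. If it is the end of the trial, the rule requires knowing that the leaver is still alive, which nothing collects.

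Deaths and power are at stake in any case. The validity of the hazard ratio and of the type I error is at stake as well if the patients who leave differ in prognosis and the arms lose different proportions. Section 7 leaves details to the SAP, but no SAP can supply vital status that the sites were never asked to obtain.

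**Working it through.** **1. The plan's own figures.** Inputs from 7.1: "comparison of two survival curves using the one-sided log-rank test"; "Type one error 0.025, power 0.80, recruiting time 6 months, length of follow up period 18 months"; 18-month survival 70% and 85%; equal groups. Exponential hazard ratio = ln 0.85 / ln 0.70 = 0.456. The Lakatos log-rank method with 6 months of accrual and at least 18 months of follow-up gives 106 per arm (power 80.2%), as stated. Inflation: 212 / 0.85 = 249.4, so 250; 250 / 0.90 = 277.8, so 278. Both reproduce. The number at issue is 0.15 × 250 = 37.5, about 38 patients.

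**2. Loss if censoring is non-informative** (design effect, 125 per arm, 18 months each as in 3.1).
- All followed: 125 × 0.30 + 125 × 0.15 = 56.25 deaths; Lakatos power 81.3%.
- 15% exponential drop-out by month 18, drop-out hazard −ln 0.85 / 18 = 0.00903 per month. Deaths per arm = 125 × λ/(λ + η) × (1 − S × 0.85), where λ is the death hazard, η the drop-out hazard and S the 18-month survival.
  - Control: λ = −ln 0.70 / 18 = 0.01982, giving 125 × 0.687 × (1 − 0.595) = 34.8.
  - Rasagiline: λ = η, giving 125 × 0.5 × (1 − 0.7225) = 17.3.
  - Total 52.1; power 78.3%.
- With the 18 to 24 months of follow-up behind the figure of 106: 64.1 deaths and 86.2% against 58.7 deaths and 83.0%.

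The loss is therefore about 4 to 5 deaths and 3 points of power.

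**3. Bias if leaving is related to prognosis.** The protocol gives no figures for this, so everything here is assumed. There is no true effect, 30% die in each arm, and 75 deaths are expected in 250.

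*Model A.* A share q of the drop-outs would have died by month 18, and they leave at a uniform time before death or month 18.

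| Drop-out placebo / rasagiline | q | Observed deaths | Apparent HR |
|---|---|---|---|
| 15% / 15% | 30% | 75 − 37.5 × 0.30 = 63.75 | 1.00 |
| 15% / 15% | 45% | 58.1 | 1.00 |
| 15% / 15% | 60% | 52.5 | 1.00 |
| 10% / 20% | 30% | 33.75 + 30.0 | 0.94 |
| 10% / 20% | 45% | 31.9 + 26.25 | 0.87 |
| 10% / 20% | 60% | 30.0 + 22.5 | 0.79 |

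In the lower three rows, deaths per arm are 37.5 − 12.5q on placebo and 37.5 − 25q on rasagiline. The row with q = 30% is already mildly informative: at the planned control hazard, a patient leaving at month 9 would die by month 18 with probability 1 − √0.70 = 16%.

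*Model B.* Drop-outs come from a 30% subgroup with three times the hazard and are assigned leaving times uniform over 0 to 18 months. The percentages are shares assigned to drop out; some die first, so an assigned 15% means about 11% actually leaving.
- Assigned 15% / 15%: HR 1.00, type I error 2.5%.
- Assigned 10% / 20%: HR 0.96, one-sided type I error 3.3% to 4.0% across repeated simulations.
- The same 10% / 20% case with leavers followed to month 18: HR 1.00, type I error 2.4%.

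**The case against.** The other side has good points.

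- **Not everything stops at exit.** Ongoing serious adverse events are followed even after the trial, adverse events are collected for 14 days, and later serious events judged possibly related go to the sponsor. The bar on rejoining prevents re-entry, not an enquiry about vital status. This stands, so it would be wrong to say that nothing more is collected. But none of these provisions establishes survival to month 18.
- **The sentence on dates of death states an intent.** That also stands; the defect is that no procedure supports it.
- **Drop-out was budgeted.** The increase from 212 to 250 covers part of the power loss. It does nothing about bias.

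A reader might infer that about 15% of patients will be informatively censored. The protocol does not support that: the rate is not defined, not equated with stopping treatment and not linked to prognosis. The reasons listed in 3.7.3 include some unrelated to disease course, such as a change of address.

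A reader might also infer that any difference in drop-out between arms biases the test. It does not, unless leaving is also related to prognosis. Equal drop-out left the HR at 1.00 in both models and mainly cost events.

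Finally, "Survival / date of death requiring a death certificate" in section 6.1 might be read as discarding deaths without a certificate. It names a source document and does not say that uncertified deaths are excluded.

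**Conclusion.** The gap is real and concerns the only confirmatory test. The protocol merges stopping medication with leaving the study, specifies no survival ascertainment to month 18 afterwards, and leaves the censoring date undefined. Sections 3.7.3, 5.1 and 5.3 therefore need to be reconciled with 2.1 and 7.3.1.

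The firm part of the size is modest: about 4 to 5 deaths and 3 points of power (81.3% to 78.3% with 18 months each), assuming 15% exponential, non-informative drop-out, and partly budgeted.

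The bias is conditional. With no true effect and assumed drop-out of 10% on placebo and 20% on rasagiline, the apparent HR runs from about 0.96 down to 0.79. One-sided type I error is about 3% to 4% against the nominal 2.5% in the mildest of these scenarios. These are sensitivity figures, not forecasts. Confidence is high that the procedure is missing; the protocol does not allow an estimate of how much bias would follow. The change is worth making because missed vital status may be unrecoverable later and the remedy is small.

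**What to change.** - **3.7.3, 5.1 and 5.3:** separate stopping study medication from objecting to further contact. State that the first does not end survival follow-up.
- **Data collection:** for every randomised patient who does not object, ascertain vital status and any date of death at month 18 after randomisation, on treatment or not. Use a call to the patient, a relative or the primary physician, as consent allows.
- **7.3.1:** define the censoring date as month 18 or, where status then is unknown, the last date known alive. Count deaths after treatment discontinuation in the ITT analysis. Keep the statement that dates of death will be known, and tie it to this procedure.

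**Cost:** a protocol amendment, possibly an addition to the consent form (those pages are not available here), and roughly 38 extra contacts at month 18. Telephone contact with the patient or a relative is already in use, but the last scheduled call is at month 15, so the month-18 contact is new. The change adds data collection only and does not alter treatment.
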